11 PHARMACOKINETIC SAMPLING

Pharmacokinetic blood samples will be collected on Cycle 1 Day 1 4 hours after completion of birinapant infusion and on Cycle 1 Day 2 at 24 hours after completion of birinapant infusion. On Cycle 1 Day 8, pharmacokinetic blood samples will be collected before the dose of birinapant, and 4 hours after completion of birinapant infusion (Table 16).

Table 16 Timing of Pharmacokinetic Sampling

Birinapant Infusion (Cycle 1 Day 1)	
Sample 2	4 hours after completion of birinapant infusion
Birinapant Infusion (Cycle 1 Day 2)	
Sample 3	24 hours after completion of birinapant infusion
Birinapant Infusion (Cycle 1 Day 8)	
Sample 4	Prior to birinapant infusion
Sample 5	4 hours after completion birinapant infusion

All blood samples will be collected from the arm opposite the site of infusion or distal to the site of infusion, in collection tubes containing K₂EDTA. If there is a delay in completion of birinapant infusion, this must be noted in the CRF. If birinapant infusion is resumed to completion, PK sample collection will continue with end of infusion and post-infusion timepoints.

Blood samples (2mL) for pharmacokinetic analyses will be drawn into pre-labeled tubes containing K₂EDTA anticoagulant at the time points specified in Table 16. Within 30 minutes of collection, blood samples will be centrifuged under refrigeration (approximately +4°C at 1500 g RCF) for approximately 10 minutes. Plasma will be harvested and divided into 2 separate aliquots. Samples will be stored frozen (-70°C preferred, or -20 °C - for specifications see Laboratory Manual) in pre-labeled cryovials prior to bioanalysis.

12 STATISTICAL CONSIDERATIONS

12.1 General Considerations

Details of the scope and nature of statistical analyses to be utilized in analyzing data from this study will be found in the Statistical Analysis Plan (SAP). The analysis of all the safety and pharmacodynamic parameters will be performed by Medivir or its designee.

Safety analyses will include all patients who receive at least one dose of either investigational product. All data collected for these patients will be used in the analyses, and no imputation will be performed for missing data. AEs that are unrelated to treatment and that occur more than 30 days after treatment administration will not be reported or analyzed. The statistical methods employed in this protocol will be primarily

descriptive since the study was not sized for a specific level of power. No inferential statistics will be utilized in the safety analyses.

For all analyses, baseline is defined as the last measurement for a variable before the dose of pembrolizumab or birinapant. All data collected on the eCRF will be included in data listings. Routine data listing or tabulation review during the study conduct will be performed to identify missing data, anomalies, and outliers.

Unless otherwise stated, continuous variables will be summarized using number of observations, mean standard deviation, median (as appropriate), minimum, and maximum. Categorical variables will be tabulated with frequencies and percentages.

All analyses will be performed using SAS® version 9.3 or later (SAS Institute, Cary NC), or comparable software. A complete description of data handling rules and planned statistical analyses will be detailed in a separate SAP before conducting any planned analysis.

12.2 Determination of Sample Size

No formal sample size or power calculations will be performed for the dose-escalation phase of the study. A sample size of 3 to 6 patients per cohort is a feasible sample size to assess safety for dose escalation and dose-limiting toxicity. Additional patients may be needed for cohort expansion during dose escalation, for the replacement of non-evaluable patients. Only patients who do not complete the first cycle due to study drug related toxicity will be replaced.

Once the RP2D of birinapant combined with pembrolizumab is defined, additional patients with relapsed or refractory carcinoma will be enrolled in the dose-expansion phase of the study.

The dose expansion phase will comprise 4 cohorts of 26-30 patients, as follows:

- Colorectal cancer (28 patients)
- Ovarian cancer (27 patients)
- Cervical cancer (26 patients)
- Various solid tumors (30 patients, including 5 patients with each of the 6 following tumor types: (Small cell lung cancer; Cholangiocarcinoma; Gastroesophageal carcinoma; Mesothelioma; Head and Neck Squamous Cell Carcinoma (HNSCC)-checkpoint inhibitor-naïve; and HNSCC checkpoint inhibitor-experienced)

A Simon's 2-stage design (Simon 1989) will be used for each of the cohorts in colorectal cancer, ovarian cancer and cervical cancer, as outlined in Table 17. A predefined interim analysis allowing stopping each of these cohorts for futility and safety will be conducted in the first stage to limit undue exposure before further inclusion into a given cohort.

The interim analyses will be based on at least 6 and most 13 patients having completed from 9 up to 27 weeks of treatment (3 to 9 cycles) in the colorectal cancer cohort and based on at least 6 and at most 16 and 15 patients in the ovarian cancer cohort and

cervical cancer cohort, respectively. Note that one additional patient will be included in each cohort. This patient will only be included in the interim analysis in case a patient drops out in that cohort. Thus, the number of included patients in each cohort will be 27+1 (CRC), 26+1 (ovarian) and 25+1 (cervical). In all cases this extra patient will be included in the main/end analysis. If the predefined level for success in a given cohort is reached prior to the stipulated number of patients being enrolled/completed, enrollment in that cohort may be discontinued.

The Simon's two-stage design yields a type I error rate of 0.05 and statistical power of 0.80 for each of the three main cohorts described above using a one-sided test when the true response rate is 20% for colorectal cancer, 25% for ovarian cancer and 30% for cervical cancer. No formal sample size or power calculation will be performed for the fourth cohort.

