3.1.1 Description of Study Design Dose Escalation Phase

The dose escalation phase of this study will employ a sequential group dose-escalation design to determine the dose-limiting toxicity (DLT) and RP2D of birinapant administered in combination with pembrolizumab, both administered as a 30-minute intravenous (IV) infusion. Pembrolizumab will be administered first on Day 1. The birinapant infusion will begin 30 minutes (+10 minutes) following the completion of the pembrolizumab infusion on

Day 1. An additional dose of birinapant only will be administered on Day 8. The dose levels of birinapant and pembrolizumab are outlined in [Table 2](#).

Table 2 Dose Escalation Schedule

Dose-Escalation Schedule	
Dose Level	Pembrolizumab + Birinapant (per 21-day cycle)*
Level -1	200 mg pembrolizumab on Day 1 + birinapant 2.8 mg/m²/week on Days 1 and 8
Level 1	200 mg pembrolizumab on Day 1 + birinapant 5.6 mg/m²/week on Days 1 and 8
Level 2	200 mg pembrolizumab on Day 1 + birinapant 11 mg/m²/week on Days 1 and 8
Level 3	200 mg pembrolizumab on Day 1 + birinapant 17 mg/m²/week on Days 1 and 8
Level 4	200 mg pembrolizumab on Day 1 + birinapant 22 mg/m²/week on Days 1 and 8

*Note: A week without treatment (i.e., Days 15-21) will follow the second week of treatment, immediately after which the next 21-day cycle commences.

A minimum of 3 and up to 6 evaluable patients will be enrolled per dose level. For patients enrolled in Dose Level 1, the birinapant starting dose will be 5.6 mg/m²/week. Dose escalation of birinapant will occur in up to three steps. The Safety Review Committee (SRC) will review all the cumulative safety data up to and including completion of Day 21 for the last patient in a cohort from that treatment group prior to dose escalation. Upon review of the safety data the SRC will determine whether or not the safety data supports dose escalation to the next sequential dose level. If the first dose level (5.6 mg/m²) is deemed intolerable, defined as ≥ 2 patients from 3-6 experiencing a DLT, the SRC may decrease the starting dose of the next dosing cohort to 2.8 mg/m² (dose level -1).

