3.1.3 Safety Review Committee Dose Escalation Phase

A SRC will be involved in the conduct of the dose escalation phase of this study. The SRC will be comprised of representatives from the Sponsor and the study sites, and the SRC may recommend that the study be interrupted or terminated at any time if, in their judgment, serious or unexpected AEs of sufficient concern warrant such action. See reporting requirements ([Section 8.3](#)) for Serious AEs (SAEs). The SRC has the responsibility for monitoring the clinical study's progress and the safety of the participating patients

Following completion of a dosing level, an evaluation of the safety of that dose will be performed by the SRC (based on cumulative data to the time of SRC assessment). The SRC will review the safety, efficacy and pharmacodynamic data (when available) from all patients enrolled at each dose level to confirm any DLTs that were experienced and to make a recommendation regarding enrollment in the next dose level. Each of the 3 to 6 patients at a dose level must have completed Cycle 1 (21-day cycle) to be eligible for SRC review. On the basis of the findings, the committee will have several options:

1. Recommend escalation to the next dose level,
2. In case of unexpected or unacceptable toxicity during the dose escalation phase recommend early discontinuation of the study, or
Alter the subsequent dose as per the dose escalation criteria presented in [Section 5.4](#).

The SRC will make the decision on RP2D based on an MTD of the combination being the occurrence of greater than 2 defined grade 3 or above SAEs (for definition of DLTs see section 5.4) in the final cohort of 3 plus 3 subjects. In the absence of an MTD, the SRC will consider pharmacodynamic and PK of birinapant as applicable considering that birinapant monotherapy has been studied previously at 10 to 63 mg/m². Doses > 47 mg/m² will not be considered.

Further details on the SRC procedures are presented in the SRC-charter

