5.4 Dose-Limiting Toxicity and Recommended Phase 2 Dose

The inter-patient dose escalation of birinapant will be based on the number of patients that experience a DLT. A DLT is a clinically significant event attributed to birinapant, pembrolizumab, or the combination of the 2 study drugs, during the first cycle of drug therapy and is defined as follows:

Non-hematological toxicity:

- Common Toxicity Criteria for Adverse Event (CTCAE; 4.03) Grade 3 nausea, vomiting, or diarrhea despite maximal (according to treating investigator) anti-emetic or anti-diarrheal treatment and lasting > 48 hours; or Grade 4 vomiting or diarrhea;
- \geq Grade 3 other non-hematological toxicity, excluding isolated laboratory abnormalities without clinical sequelae, except for the following:
 - Prolonged (> 7 days) serum amylase or lipase elevation;
 - Prolonged (> 7 days) aspartate aminotransferase (AST) elevation;
 - Prolonged (> 7 days) alanine aminotransferase (ALT) elevation;All of which will be considered dose limiting.

Hematological toxicity:

- Grade 4 neutropenia;
- Grade \geq 3 neutropenia with fever > 38.3°C or > 38°C (> 100.9°F or > 100.4°F) for more than one hour;
- Grade \geq 3 thrombocytopenia with bleeding

Specific toxicity:

- Cytokine release syndrome (CRS); Grade 3 or 4. Furthermore, if a Grade >2 CRS occurs during the DLT period (Cycle 1), this also triggers the permanent discontinuation of all study dosing (birinapant AND pembrolizumab) with subsequent adequate care to treat the condition (see also sections 5.5.1 and 5.5.3).

If Day 8 of treatment is held due to toxicity then the event will be considered a DLT. A prolonged delay (> 2 weeks) in initiating Cycle 2 secondary to drug-related toxicity may be considered a DLT as judged by the SRC. Events related to disease progression, intercurrent illness, or concomitant medication will not constitute a DLT. Since patients are assessed for DLTs during the first cycle, dose modifications may not be performed. If a patient experiences a DLT that is deemed related to birinapant, the dose of birinapant may be restarted at a reduced level for Cycle 2 according to dose levels indicated in Table 2/[section 3](#) and the rules stated in [section 5.5](#), and the patient may remain on study.

The decisions to dose-escalate birinapant for each Dose Level are indicated in [Table 5](#) below.

Table 5 Escalation Decision Rules

Number of Patients with DLT at a Given Dose Level	Escalation-decision Rule

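### Protocol 12.2 states the dose-escalation replacement rule the wrong way round, and the MTD limit in 3.1.3 that drives the RP2D does not match the intolerable-dose rule used elsewhere

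*Protocol*

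**What the plan says.** **Replacement.** Protocol 12.2 first gives the purpose: "Additional patients may be needed for cohort expansion during dose escalation, for the replacement of non-evaluable patients". The next sentence sets the rule: "Only patients who do not complete the first cycle due to study drug related toxicity will be replaced". Protocol 3.1.1 requires that "A minimum of 3 and up to 6 evaluable patients will be enrolled per dose level", and SAP 3.1.1 repeats it. SAP 3.3.1.1, on the escalation sample size, contains no replacement rule.

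Protocol 5.4 defines a DLT as a drug-attributed event in Cycle 1 and adds: "If Day 8 of treatment is held due to toxicity then the event will be considered a DLT". Grade 3 or 4 cytokine release syndrome is also a DLT, and in Cycle 1 it requires both drugs to be stopped for good. Events put down to progression, another illness or other medicines are not DLTs.

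Protocol 3.1.3 has the Safety Review Committee (SRC) look at data "from all patients enrolled at each dose level to confirm any DLTs that were experienced". It then says: "Each of the 3 to 6 patients at a dose level must have completed Cycle 1 (21-day cycle) to be eligible for SRC review".

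**MTD and RP2D.** Protocol 3.1.3 states that "The SRC will make the decision on RP2D based on an MTD of the combination". The limit it gives for that MTD is "greater than 2 defined grade 3 or above SAEs (for definition of DLTs see section 5.4) in the final cohort", meaning the last 3+3 group. The synopsis escalation table, Protocol 3.1.1, Table 5 in section 5.4 and SAP 3.1.1 all define an intolerable dose as 2 or more patients with a DLT among 3 to 6. Under Table 5, 2 or more DLTs stop escalation; calling the dose intolerable is then permitted, not required.

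**The concern.** In a 3+3 scheme, a patient who leaves Cycle 1 because of a DLT has given the information the scheme needs. A patient who leaves for an unrelated reason, without a DLT, has not. Section 12.2 reverses this: it replaces the first and bars replacement of the second.

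The MTD wording is a separate problem. The RP2D rests on a limit that differs from the intolerable-dose definition in both number (more than 2, against 2 or more) and unit (SAEs, against patients with a DLT). A site or committee following the text could reach different answers about the same dose. The RP2D is the starting dose for up to 111 expansion patients (28 + 27 + 26 + 30).

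**Working it through.** **The plan's own figure.** The synopsis gives up to 24 escalation patients. One starting level plus up to three steps is 4 levels, and 4 × 6 = 24, so the figure reproduces. Section 12.2 gives no power or other operating characteristics for this phase, so the DLT rates below are assumptions.

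**Replacement rule: who falls where.**

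| Patient does not finish Cycle 1 because of | Status under 5.4 | Replaced under 12.2? |
|---|---|---|
| Grade 3–4 cytokine release syndrome, drugs stopped | DLT, evaluable | Yes |
| Toxicity that holds Day 8 and ends treatment | DLT, evaluable | Yes |
| Drug-related Grade 2 toxicity after Day 8, withdrawal before Day 21 | Not a DLT | Yes |
| Progression, other illness, withdrawal of consent | Not a DLT, assessment incomplete | No |

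The first two rows need no replacement and the last does. The third row shows why a corrected rule should turn on whether the patient had a DLT, not on whether the reason was toxicity.

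The conflict with 3.1.1 depends on numbers. A level that entered 3 patients and loses one to progression has 2 evaluable and cannot reach 3 without breaking 12.2. A level that entered 4 to 6 and loses one still has at least 3.

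**MTD limit: the same data under the two rules.**

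| Cohort of 6 | Table 5 / 3.1.1 / synopsis / SAP 3.1.1 | Protocol 3.1.3 |
|---|---|---|
| 1 patient with a DLT | Not intolerable | Limit not reached unless there are 3 or more qualifying SAEs |
| 2 patients with a DLT | Meets the intolerable definition; escalation stops | Limit not reached unless there are 3 or more qualifying SAEs |
| 3 patients with a DLT | Same as for 2 | Reached only if there are 3 or more qualifying SAEs |

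A DLT need not be a Grade 3 or higher SAE: a Day 8 dose held for toxicity counts under 5.4 whatever its grade or seriousness. The pointer to 5.4 inside the 3.1.3 criterion does not reconcile the two units.

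**How often 2 in 6 could arise.** Take the path of 1 DLT in the first 3 patients, then 1 in the next 3, at one level with true DLT rate p. This assumes that a level with 1/3 is filled to 6.

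- P(1 of 3) = 3p(1−p)²: 0.384, 0.441, 0.432 at p = 0.2, 0.3, 0.4.
- P(1/3 then 1/3) = [3p(1−p)²]²: 0.147, 0.194, 0.187, that is 15%, 19%, 19%.
- An observed 2/6 is 33%, exact (Clopper–Pearson) 95% CI 4% to 78%.

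Protocol 3.1.1 and SAP 3.1.1 can also be read as moving to the next level at once after a single DLT. The path then arises only if the level is filled to 6 later, as 3.1.1 requires once the next higher dose has been found intolerable.

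**The case against.** A reader might infer from 12.2 that replaced patients' DLTs drop out of the count, so that escalation is too easy. The documents do not support this. Table 5 counts patients with a DLT, 3.1.3 has the SRC consider all enrolled patients, and section 12.1 keeps everyone who received a dose in the safety analyses. The Cycle 1 completion sentence in 3.1.3 sits awkwardly with this but does not override it. No undercounting is claimed.

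A reader might also infer that 3.1.3 permits a dose with 2 DLTs in 6 to be the RP2D. It does not say so. It gives an MTD criterion that such a dose need not meet, and it refers dose changes back to 5.4. Nor does Table 5 give a firm prohibition, since its wording is permissive. The supportable statement is that the question is left open. The SRC charter, not available here, may settle it.

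The remaining objections concern weight:

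- The replacement conflict bites only when fewer than 3 evaluable patients remain.
- The SAP's silence is not a further defect, because it leaves design detail to the protocol.
- Section 1.6.1 puts the single-agent MTD at 47 mg/m² weekly and reports up to 22 mg/m² weekly, the top level here, already used with chemotherapy.
- During expansion, birinapant can be reduced and the DMC can reappraise the MTD or RP2D.

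These points limit the harm. They do not correct the protocol text, and DMC review comes after expansion has begun.

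**Conclusion.** Both rules are wrong as written and should be fixed. That the texts conflict is certain; the consequence is less so. The replacement rule selects largely the wrong patients and contradicts the preceding sentence. It makes the 3-evaluable minimum unattainable only when a non-toxicity loss leaves fewer than 3, and no effect on escalation probabilities is shown or claimed.

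The MTD mismatch is the part that could affect dose selection. The escalation decision at 2 DLTs is clear; the RP2D decision is not. The 15% to 19% is the probability of one observed path at one level, on assumed DLT rates of 20% to 40% and with the level filled to 6. It does not measure how often the SRC would carry such a dose forward.

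**What to change.** In Protocol 12.2, replace the sentence with: *Patients who do not complete Cycle 1 for any reason other than a DLT, and who have not had a DLT, are non-evaluable and will be replaced. Every patient with a Cycle 1 DLT is evaluable, stays counted at that dose level and is not replaced.*

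In Protocol 3.1.3, change the review-eligibility condition to *completed Cycle 1 or had a DLT*, and restate the MTD criterion as *2 or more patients with a section 5.4 DLT among 3 to 6*. Check the SRC charter for the same wording.

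The cost is a few sentences and possibly a few more patients. If all 24 places had to be evaluable, expected replacements are 24d/(1−d) = 1.3, 2.7 or 6.0 at assumed Cycle 1 losses without a DLT of d = 5%, 10% or 20%. The limit of 24 needs no rewording: Protocol section 4 already calls it approximate, and 12.2 already allows for additional patients.

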12.4 Analysis Population

The following four populations will be defined for this study:

- Intent-to-Treat Population (ITT): will comprise any patient that is enrolled to the study and receives a dose of pembrolizumab and birinapant. Note that the ITT population can be considered equivalent to the Full Analysis Set population as no randomization is done in this study.
- Safety Population: will be the same as the ITT population.
- Efficacy Evaluable Population: will comprise all patients in the ITT population who have baseline and at least one post-baseline efficacy assessment, unless the patient dies or experiences an AE that results in study drug termination prior to assessment. At that point, the patient will be considered to have progressed in the absence of other data.
- Pharmacodynamic Population: The pharmacodynamic population will include all treated patients for whom pre- and post- infusion pharmacodynamic data are available.

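### Protocol 12.2 states the dose-escalation replacement rule the wrong way round: it replaces patients lost from Cycle 1 to drug toxicity and bars replacing anyone else (minor)

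*Protocol*

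**What the plan says.** Protocol 12.2 gives no formal sample size for dose escalation. It says that additional patients may be needed "for the replacement of non-evaluable patients", and its next sentence on the subject is "Only patients who do not complete the first cycle due to study drug related toxicity will be replaced".

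Other sections bear on the same patients:

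- 3.1.1: "A minimum of 3 and up to 6 evaluable patients will be enrolled per dose level".
- 3.1.3: each of the 3 to 6 patients at a level "must have completed Cycle 1 (21-day cycle) to be eligible for SRC review". The same section has the SRC review data "from all patients enrolled at each dose level to confirm any DLTs that were experienced".
- 5.4: "The inter-patient dose escalation of birinapant will be based on the number of patients that experience a DLT". Table 5 then acts on zero, one, or two or more patients with a DLT among 3 to 6. Holding the Day 8 dose for toxicity is itself a DLT. Grade 3 or 4 cytokine release syndrome (CRS) is a DLT, and in Cycle 1 "this also triggers the permanent discontinuation of all study dosing". Events due to progression, intercurrent illness or concomitant medication are not DLTs.
- 12.4: "The following four populations will be defined for this study". None of the four is a DLT-evaluable set.

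SAP 3.3.1.1 repeats the sample-size statement for this phase but carries no replacement rule.

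**The concern.** Escalation rests on a count of patients with a DLT among 3 to 6, so the protocol has to fix who belongs in that group. The usual logic is that a patient with a DLT has given the answer and stays in, while a patient who leaves early without one has not and is replaced. Section 12.2 reverses both halves. It attaches replacement of the non-evaluable to the patients most likely to have had a DLT, and the word *only* shuts out the patients who are in fact not assessable.

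At stake is whether sites and the SRC work to one rule. The escalation phase selects the dose given to every patient in the expansion cohorts, and DLT incidence is part of its safety assessment. The Simon two-stage settings for the expansion phase are not affected.

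**Working it through.** The plan's one figure for this phase reproduces. The synopsis gives up to 24 patients. Level 1 plus up to three escalation steps makes 4 levels, and 4 × 6 = 24. That total contains no separate allowance for replacements.

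The rest is a comparison of texts, taken by type of patient who does not finish Cycle 1.

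1. **Stopped for Grade 3 or 4 CRS.** 5.4 makes this a DLT and ends dosing with both drugs. 12.2 says replace. Table 5 says count. Nothing states whether the replacement then joins the same group of 3 to 6, so the denominator is unclear.

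2. **Leaves through progression, intercurrent illness or withdrawal of consent.** The first two are excluded as DLTs by 5.4, and a withdrawal is not a toxicity. 12.2 does not allow replacement. With 3 enrolled and one such loss, 3 − 1 = 2 patients are fully assessed, below the minimum of 3 evaluable in 3.1.1, and the third has not completed Cycle 1 as 3.1.3 requires. 12.2 withholds the replacement that the other two sections need.

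3. **Receives Day 8, then leaves for related toxicity below the DLT threshold.** 12.2 says replace, and here that is right: there is no DLT and no complete Cycle 1. The group is narrow. A patient whose Day 8 dose is held for toxicity already has a DLT under 5.4, so this case arises essentially only after Day 8.

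So 12.2 gives the wrong instruction for types 1 and 2 and the right one only for type 3. Most of the patients it would replace are of type 1 or have another DLT.

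The texts that might settle the matter do not. 12.4 has no DLT-evaluable population, *evaluable* is not defined for DLT purposes, and the SAP leaves the rule out. 3.1.3 refers to an SRC charter for further procedure. The charter is not among the documents, and it would not correct the protocol sentence in any case.

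**The case against.** **A reader might infer that DLTs go uncounted.** The documents do not support this. 12.2 is about extra accrual and never says that a replaced patient's DLT is dropped. Escalation is governed by 5.4 and Table 5, which count patients with a DLT, and 3.1.3 puts all enrolled patients before the SRC. 12.6 bases safety on DLT incidence in the ITT population, which under 12.4 includes anyone who received both drugs. This objection stands: replacing such a patient is odd, but it does not hide the event.

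**A reader might infer that 3.1.3 keeps a patient with a DLT out of SRC review.** That needs completing Cycle 1 to mean completing its dosing. The CRS rule stops dosing, not follow-up. Under 4.3, adverse events are assessed for up to 30 days after the last dose. Even after a single Day 1 dose this reaches Day 1 + 30 = Day 31, beyond the Day 21 data point for review in 3.1.1. Completing the 21-day observation is a fair reading, so 3.1.3 is ambiguous here and not in plain conflict.

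**A reader might infer that levels will be judged on two assessed patients, with a higher chance of escalating.** 3.1.1 and 3.1.3 both oppose judging such a level, and a level may hold up to 6, so a fourth patient could enter without being called a replacement. The documents also give no DLT rate or dropout rate. No escalation probability is therefore offered.

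What survives is the sentence itself. The room to add a patient comes from other sections; 12.2 still forbids replacing the patient who needs it and prescribes replacing the one who does not.

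**Conclusion.** The replacement rule in 12.2 is wrong as written, and it contradicts the requirement of 3.1.1 for 3 evaluable patients and of 3.1.3 for completed Cycle 1. The firmer half is the bar on replacing patients who leave for reasons other than toxicity, because it does not depend on how a replaced patient's DLT is handled. The other half is a mismatch with Table 5 that leaves the denominator unclear.

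The severity is minor. No undercount of DLTs is shown and no size is claimed. The conclusion rests on reading *only* in its ordinary sense and on the documents provided; the SRC charter could limit the practical effect.

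**What to change.** In Protocol 12.2, replace the sentence with: *Patients who do not complete Cycle 1 for any reason other than a DLT are non-evaluable for DLT and will be replaced. A patient with a DLT is evaluable, is counted in Table 5 and is not replaced.* The phrase *for any reason other than a DLT* matters. Wording such as *other than drug-related toxicity* would leave the type 3 patient neither replaced nor counted as having a DLT.

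In Protocol 3.1.3, change the condition for SRC review to: *must have completed Cycle 1 or had a DLT*. The sentence in 5.4 on a held Day 8 dose needs no change.

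The cost is two wording changes, a matching line in the SRC charter if it needs one, and possibly a few extra replacement patients.
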